Baseline work-up (per NCCN guideline) within 28 days +/- 14 days prior to enrollment: CBC with Diff, CMP, Calcium, Albumin, Serum Protein analysis, Quantitative Immunoglobulin, Serum Immunofixation (SIFE), 24 hr urine total protein, Urine Immunofixation, Serum Free Light Chain, Bone Marrow Biopsy (with IHC, flow, cytogenetics, FISH),

Whole Body PET/CT, Biopsy of Osseous or extra-osseous site (only if clinically indicated);
Pregnancy test;

Inclusion Criteria:

- 1) ≥ 18 years old; ISS stage I-III multiple myeloma that has progressive, relapsed, or refractory disease;
- 2) Able to give informed consent;
- 3) ECOG 0-1;
- 4) Relapsed and/or refractory myeloma; There is no minimum or maximum number of previous therapies that a patient may have received previously before being put on the current trial.
- 5) ≥ 1 osseous and/or extra-osseous lesion that can be radiated;
- 6) Candidate for pembrolizumab (as determined by physician, and adequate organ function as noted in **Table 1**);
- 7) Candidate for radiotherapy (as determined by treatment physician); These patients can have symptomatic disease and/or asymptomatic disease. A minimum of one site of radiation is required to any osseous and/or any extra-osseous disease. Radiation to any bony parts of the Head and Neck, Skull, Spine, ribs, and/or extremities are allowed. Radiation to any bony part for documented lytic disease is allowed. Radiation to any soft tissue plasmacytoma (including osseous and extra-osseous plasmacytoma) is allowed. The only exclusion criteria for radiation, is CNS metastases (see exclusion criteria # 16);
- 8) Measurable myeloma disease (**urine protein > 200 mg in 24 hr urine collection, serum free light chain ratio > 100 with an abnormal k/l ratio, serum M protein > 0.5 g/dl**) ; **12 of the 24 patients do not have to have measurable disease;**
- 9) Negative urine pregnancy test within 2 weeks for female subjects;

Female subjects of childbearing potential should have a negative urine or serum pregnancy within 72 hours prior to receiving the first dose of study medication. If the urine test is positive or cannot be confirmed as negative, a serum pregnancy test will be required.

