It is unknown whether pembrolizumab is excreted in human milk. Since many drugs are excreted in human milk, and because of the potential for serious adverse reactions in the nursing infant, subjects who are breast-feeding are not eligible for enrollment.

Subject Withdrawal/Discontinuation Criteria

Subjects may withdraw consent at any time for any reason or be dropped from the trial at the discretion of the investigator should any untoward effect occur. In addition, a subject may be withdrawn by the sponsor-investigator if enrollment into the trial is inappropriate, the trial plan is violated, or for administrative and/or other safety reasons.

A subject must be discontinued from the trial for any of the following reasons:

8. The subject or legal or legal representative (such as a parent or legal guardian) withdraws consent.
9. Confirmed extra- extra-cranial radiographic disease progression.
10. Unacceptable adverse experiences as described in section 6 and 7.
11. Intercurrent illness that prevents further administration of treatment.
12. Investigator's decision to withdraw the subject.
13. The subject has a confirmed positive serum pregnancy test.
14. Noncompliance with trial treatment or procedure requirements.
15. The subject is lost to follow-up.
16. Completed at least 24 months of uninterrupted treatment with pembrolizumab or 35 administrations of study medication, or whichever occurs last;

Note: 24 months of study medication is calculated from the date of first dose. Subjects who stop pembrolizumab after 24 months may be eligible for up to one year of additional study treatment at the discretion of their treating physician, especially if their disease is clinically stable;

17. Administrative reasons
18. Confirmed radiographic disease progression per RECIST criteria
 1. *Note: A subject may be granted an exception to continue on treatment with confirmed radiographic progression if clinically stable or clinically improved, please see Section 6 and 7.*

The End of Treatment and Follow-up visit procedures are listed in Section 10 (Protocol Flow Chart) and Section 11. After the end of treatment, each subject will be followed for 30 days for adverse event monitoring (serious adverse events will be collected for 90 days after the end of treatment). Subjects who discontinue for reasons other than progressive disease will have

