APPENDIX III

Tumor Assessment per Immune-Related Response Criteria

Immune-related Response Criteria (irRC) are derived from modified World Health Organization (mWHO) conventions. Assessments of lymph nodes are derived from current RECIST guidelines.

a.) Definitions of Measurable/non-Measurable Lesions

All measurable and non-measurable lesions should be assessed at the initial Screening/enrollment, at the defined tumor assessment time points (see Time and Events Schedule), and during regular maintenance. Additional assessments may be performed, as clinically indicated for suspicion of progression. The Investigator will base response to treatment using the irRC.

i.) Measurable Disease

Measurable non-lymph node disease is defined as lesions that can be accurately measured in 2 perpendicular Diameters. Size criteria is defined based on the properties of the CT scan

- Spiral CT, 0.5cm thickness slice: both diameters must be at least $\geq 1.0\text{cm}$
- For $> 0.5\text{cm}$ thickness slices: larger diameter $>2.0\text{cm}$; the other $> 1.0\text{cm}$

Lymph nodes are measurable only if CT slice thickness is $<0.5\text{cm}$. Size criteria are that the lymph node be at least 15 mm in short axis.

ii.) Non-Measurable Lesions

Non-measurable (evaluable) lesions are all other lesions, including one-dimensional measurable disease and small lesions (not meeting the above criteria), and any of the following:

- lesions occurring in a previously irradiated, extracranial area (unless they are documented as new lesions since the completion of radiation therapy),

bone lesions,
-leptomeningeal disease,
-ascites,
-effusion (pleural or pericardial)
-cystic lesions
-abdominal masses not histological confirmed

Lymph nodes with a short axis < 10 mm are considered not pathological, and are not measurable.

b.) Definitions of Index/non-Index Lesions

i.) Index Lesions

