Measurable lesions, up to a maximum of 5 lesions per organ and ten lesions in total, must be identified as index lesions to be measured at Screening. The index lesions should be representative of all involved organs. In addition, index lesions must be selected based on their size (e.g., lesions with the longest diameters), their suitability for accurate repeat assessment by imaging techniques, and how representative they are of the subject's tumor burden. At Screening, a Sum of the Product Diameters (SPD) for all index lesions will be calculated and considered the baseline SPD. The baseline sum will be used as the reference point to determine the objective tumor response of the index lesions at tumor

assessment.

ii.) Non Index Lesions

Measurable lesions, other than index lesions, and all sites of non-measurable disease, will be identified as non-index lesions. Non-index lesions will be evaluated at the same assessment time points as the index lesions. *After the initial assessment, changes in non-index lesions will contribute only in the assessment of complete response.*

c.) Calculation of Sum of Product of Diameters (SPD)

Sum of Product of Diameters is an estimate of tumor burden. The 2 greatest perpendicular diameters are used to estimate the size of each tumor lesion. The SPD is calculated as the sum of the product of the diameters for index tumor lesions. Several variations of the SPD are identified for the purpose of classification of tumor responses.

i.) SPD at Baseline

The sum of the product of the diameters for all index lesions identified at baseline prior to treatment on Day 1.

ii.) SPD at tumor assessment

For every on-study tumor assessment collected per protocol or as clinically indicated, the SPD at tumor assessment will be calculated using tumor imaging scans. All index lesions and all new measurable lesions that have emerged after baseline will contribute to the SPD at tumor assessment (irSPD).

iii.) SPD at NADIR

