For tumors that are assessed more than 1 time after baseline, the lowest value of the SPD (SPD Baseline or SPD at tumor assessment) is used to classify subsequent tumor assessments for each subject. The SPD at tumor assessment using the irRC for progressive disease incorporates the contribution of new measurable lesions. Each net percentage change in tumor burden per assessment using irRC accounts for the size and growth kinetics of both old and new lesions as they appear. In this study the irRC as defined by the Investigator will serve as the basis of key endpoints for efficacy analyses and guide clinical care.

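### The mandatory discontinuation list uses radiographic and RECIST progression and Appendix III uses irRC, while continuation, assessment and the response endpoints use IMWG

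*Combined protocol and SAP*

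**What the plan says.** **Discontinuation.** Section 7, Subject Withdrawal/Discontinuation Criteria, lists reasons for which a subject must come off the trial. Item 9 is "Confirmed extra- extra-cranial radiographic disease progression" and item 18 is "Confirmed radiographic disease progression per RECIST criteria". A note under item 18 lets a subject be granted an exception "if clinically stable or clinically improved, please see Section 6 and 7".

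**Appendix III.** On lesion assessment it says "The Investigator will base response to treatment using the irRC". It closes by saying that "the irRC as defined by the Investigator will serve as the basis of key endpoints for efficacy analyses and guide clinical care".

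**Everywhere else the criterion is IMWG:**
- Sections 1 and 2 (Trial Overview) keep patients with IMWG stable disease or better on maintenance pembrolizumab and remove those with progressive disease.
- Section 5 (Administration of Pembrolizumab Beyond Progression) uses IMWG on repeat myeloma labs to decide whether drug continues.
- Section 3 defines response and overall response by IMWG at 6 and 12 months.
- The Section 9.1 flow chart schedules an IMWG assessment. It has no RECIST or irRC row.
- Section 11 assesses response by IMWG.

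The data collection list (14.1) tags the PET/CT field as RECIST and names no IMWG field.

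**The concern.** Two operative texts, a mandatory stopping list and an appendix that claims to guide care, name criteria different from those that govern the rest of the trial. No order of precedence is given. What is at stake is who must stop pembrolizumab and which method a clinician uses to judge response. Progression status also decides the follow-up path: Sections 7 and 10 move a patient with progression to telephone contact for survival.

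The wording looks carried over rather than chosen. An extra-cranial qualifier does not fit a trial that allows skull irradiation and excludes patients who need radiation for CNS disease. Table 6 and Section 11 still refer to SRS.

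**Working it through.** No sample-size or endpoint figure is involved, so the check is a comparison of texts.

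**Step 1: what the list covers.** The reasons are numbered 8 to 18, so there are 18 − 8 + 1 = 11. Two concern progression (9 and 18). Neither names IMWG, and both are radiographic.

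**Step 2: apply each rule to the four possible states.**

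| Patient state | Sections 1, 2 and 5 | Section 7 items 9 and 18 | Conflict? |
|---|---|---|---|
| No progression by either | Continue | Not triggered | No |
| IMWG progression on labs only | Remove, subject to Section 5 | Not triggered | No: removed by Sections 1 and 2 |
| Progression by both | Remove, subject to Section 5 | Must stop, subject to the note | No conflict of criterion |
| RECIST or radiographic progression, IMWG stable disease or better | Continue | Must stop, subject to the note | **Yes** |

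In the last row the two instructions cannot both be followed. The note under item 18 gives a discretionary way out. Item 9 carries no note of its own. The note points to Sections 6 and 7, but Section 6 covers immune-related events and infusion reactions, and Section 7 is where the list itself sits.

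**Step 3: apply Appendix III to a patient with bone disease only.**
1. Such a patient is eligible. Inclusion criterion 5 asks for at least one "osseous and/or extra-osseous lesion that can be radiated", and Section 8 accepts a lytic bone lesion as the target.
2. Appendix III lists bone lesions as non-measurable.
3. It then says that "all sites of non-measurable disease, will be identified as non-index lesions".
4. After the first assessment, changes in non-index lesions count only towards complete response.
5. The sum of products used to follow tumour burden takes index lesions plus new measurable lesions. With bone lesions only, no lesion enters the baseline sum, and growth of existing bone lesions adds nothing later.

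Taken literally, Appendix III gives the investigator a method that cannot register growth of existing bone lesions as progression, in a disease where bone is an expected site.

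**Step 4: look for a reconciling statement.** None was found. Section 2 sends the reader to Appendix II for IMWG, but Appendix II is RECIST 1.1 and IMWG is Appendix IV. That is a wrong number rather than a rule, but it leads to the wrong criteria.

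**The case against.** **The list need not be exhaustive.** It gives sufficient reasons, so leaving out IMWG progression is an omission and not a contradiction. This stands. A reader might infer that a patient with laboratory-only progression could not be taken off treatment. The documents do not support that: Sections 1 and 2 remove patients with progressive disease, and Section 5 stops drug on repeat IMWG progression.

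**irRC is not operational.** The body of the protocol never cites Appendix III, the flow chart schedules IMWG, and Sections 3 and 11 define response by IMWG. This stands as to the analysis. A reader might infer that the response criterion is in doubt or that reported rates would shift; neither follows. It does not dispose of Appendix III's claim to guide care, or of the word must in Section 7.

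**The exception already softens item 18.** True, but it is discretionary, sits under that item only, and is poorly cross-referenced.

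**RECIST and irRC only describe PET/CT.** That may have been the intent. Section 3, however, defines overall response by IMWG, and Section 7 and Appendix III give the other criteria wider roles.

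**How many patients?** Because "12 of the 24 patients do not have to have measurable disease", a reader might infer that half the trial depends on imaging to call progression. That is not established. The criterion sets entry thresholds only; a patient below them could later exceed them or progress on marrow. Appendix IV gives IMWG only as a link.

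**Clerical slips are not contradictions.** Agreed. The appendix number, the section pointer and Section 5's reference to an earlier scan when comparing labs are corrections to make alongside, not evidence of conflicting rules.

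**Conclusion.** The plan is wrong as written: an internal inconsistency, not a design choice. The conflict is confined to patients with RECIST or radiographic progression whose disease is stable or better by IMWG, together with Appendix III's treatment of existing bone lesions.

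No numerical effect is claimed. The documents give no basis for counting the patients in the conflicting state. The primary toxicity endpoint does not use any of these criteria, and the SAP response criterion is IMWG.

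The conclusion assumes that RECIST and IMWG can disagree in a given patient. The protocol treats them as separate criteria in separate appendices, but the IMWG text is not reproduced, so the overlap cannot be measured here.

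**What to change.** 1. **Section 7 list.** Replace items 9 and 18 with one item: confirmed progressive disease per IMWG (Appendix IV), by any IMWG-accepted assessment (laboratory, imaging or marrow). Make it subject to Section 5 for laboratory progression. Keep the existing exception for clinically stable or improved patients with imaging progression as free-standing text, without the pointer to Sections 6 and 7.
2. **Appendix III.** Delete the sentences that make irRC the basis of response, endpoints and care, or limit RECIST and irRC to descriptive reading of PET/CT.
3. **Section 10, Follow-up Visits.** Keep the 4-6 week imaging confirmation and state that it applies to patients on treatment as well as off it. The paragraph opens with patients who have stopped, yet goes on to tell the reader to discontinue treatment.
4. **14.1 Data Collection.** Mark the RECIST-tagged PET/CT field as descriptive. Record IMWG response status from the assessment already scheduled in Section 9.1.
5. **Clerical corrections.** In Section 2, change Appendix II to Appendix IV. In Section 5, refer to the previous assessment rather than a scan. In Section 7, Discontinuation of Study Therapy after CR, make the retreatment trigger confirmed IMWG progression, which fits the confirmed progression required under Second Course Phase in Section 10.

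The cost is a small amendment and one data field. No visit, scan or laboratory test is added.

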8. DELIVERY OF RADIATION THERAPY TREATMENT

Patients will receive on **day 1**, radiotherapy (**8 Gy/1fx**) to an extra-osseous site and/or any bony site containing myeloma deposit, followed by pembrolizumab (**200 mg/kg i.v. on day 3**).

Radiation Simulation and Diagnostic Procedures

All simulation and treatment procedures represent **current institutional practice**, and will be the same for all study participants.

A radiation patient should have some evidence of disease on imaging prior to CT simulation. This can include a lytic lesion in a bony site or an extra-osseous disease. Lytic lesions and/or extra-osseous noted on X-Ray, CT scan, PET/CT, and/or MRI are allowed.

CT Simulation: A CT simulation using appropriate immobilization will be performed for radiation therapy treatment planning purposes several days to the initiation of radiation therapy. This procedure consists of a CT scan performed in the treatment position. It is not for diagnostic purposes and is not itself therapeutic, but the CT image is required for radiation planning and delivery.

Radiation Dose and Tumor Volume Definition

Patients will be treated per institutional standard of care protocol.

The prescribed radiation dose will be **8 Gy in 1 fraction prescribed to the planning target volume (PTV)**.

Treatment shall be delivered with megavoltage machines of a minimum energy of 4 MV photons or electron machine containing a minimum energy of 4 MeV. Selection of the appropriate photon energy should be based on optimizing the radiation dose distribution within the target volume and minimizing dose to non-target normal tissue.

The **Gross Tumor Volume (GTV)** will contain the lytic lesion and/or the extra-osseous lesion noted on the simulation CT. Image fusion to adjust the CT simulation based GTV is allowed.

The **Clinical Target Volume (CTV)** will be a **0.5- 2.0 cm margin** around the GTV.

The **Planning Target Volume (PTV)** will be an additional **0.3-1.0 cm margin** around the CTV.

Radiation Treatment Planning

Any radiation treatment planning approach is allowed. For superficial lesions amenable to electron treatments, use of En-Face electron technique is encouraged using appropriate energy

selection ranging from 4 MeV – 20 MeV. For deeper seated tumors, photon therapy should be used with energy range of 4MV – 18 MV, based on appropriate coverage of the PTV. The goals should be to provide adequate coverage, while minimizing hot spots as well as scattered radiation dose to the surrounding structures.

A range of radiation fields are allowed. A single beam, an AP/PA, or multiple beams are allowed. A range of radiation techniques (2D, 3DCRT, IMRT, IMRS) are allowed;

Institutional standard of care protocol will be followed when assessing adequate PTV coverage and dose volume histogram normal tissue limits.

Radiation Toxicity Evaluation

Patients should undergo evaluation for development of acute and chronic radiotherapy toxicity at the time of protocol visits. This should be done at **1 month +/- 2 weeks** after completing radiotherapy and **every 3 months for at least 1 year**. Toxicity will be graded per CTCAE 4.0 adverse events grading system. If there is a suspicion of a novel or unexpected toxicity of grade 3 or higher severity that is suspected to be related to the combination of pembrolizumab and radiotherapy, the study coordinator should be immediately notified. If possible, a determination should be made whether the toxicity is likely to be the result of immune therapy, radiotherapy, or was exacerbated by the combination. The AE or SAE should be attributed as definite, probable, possible, or unlikely for each.

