1. PROTOCOL SUMMARY

Abbreviated Title	Pilot Study of Pembrolizumab and Single-fraction, Low-dose, Radiation Therapy in Patients with Relapsed or Refractory Multiple Myeloma
Trial Phase	Pilot Study
Clinical Indication	Relapsed or Refractory Multiple Myeloma
Trial Type	Pilot study
Type of control	None
Route of administration	Patients will receive on day 1, cycle 1 , radiotherapy (8 Gy/1fx) to an extra-osseous or osseous myeloma site followed by pembrolizumab (200 mg/kg i.v. on day 2 or 3 , then every 3 weeks +/- 7 days).
Trial Blinding	N/A
Number of trial subjects	24 patients (20 patients minimum, with 4 extra patients to account for loss to follow-up/attrition and/or failure to comply with recommended treatments); 12 patients will be allowed to not have measurable myeloma disease.
Estimated enrollment period	2 years
Description of enrollment	Following evaluation by medical oncology and radiation oncology, patients will be enrolled. Baseline assessment prior to enrollment may include bone marrow biopsy, peripheral blood collection, and staging of the patient per standard of care. Baseline serum and urine paraprotein analysis, bone marrow biopsy, PET/CT imaging, routine blood work, and baseline physical exam prior to enrollment. Patient with measurable myeloma disease will be screened for tolerability to Pembrolizumab and radiotherapy. Patients will be assessed at 1st month and every 3 month for response using the standard International Myeloma Working Group (IMWG) Response Criteria, and will undergo routine myeloma labs every 6 weeks until progression or as clinically indicated ; Patients with stable disease or better per IMWG response criteria will continue with maintenance pembrolizumab (200 mg/kg every 3 weeks for 2 yrs) . Patients that have progressive disease, or relapse after a complete response will be removed from the trial and treated per standard of care at the discretion of the treating physician.
Duration of Intervention	At least 24 months of Pembrolizumab, or until progression.
Duration of Evaluation	3 year (2 yrs for accrual, and at least 1 year follow-up for the last patient accrued on the study)
Estimated duration of trial	3 years (2 years to accrue + 1 years to follow all patients)
Duration of Participation	3 years
Study Center	Emory University. Atlanta, Georgia.

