2. TRIAL DESIGN/SCHEMA

1. Trial Overview

Following evaluation by medical oncology and radiation oncology, patients with **measurable myeloma disease** will be enrolled. Baseline assessment prior to enrollment may include bone marrow biopsy, peripheral blood collection, and staging of the patient per standard of care. Baseline serum and urine paraprotein analysis, bone marrow biopsy, PET/CT imaging, skeletal survey, routine blood work, and baseline physical exam prior to enrollment. Patient will be screened for tolerability to Pembrolizumab, and those that are also eligible for radiotherapy will be identified.

Patients will receive on **day 1, cycle 1**, radiotherapy (**8 Gy/1fx**) to an extra-osseous site and/or any osseous bony site, followed by pembrolizumab (**200 mg/kg i.v. on day 2 or 3**). Baseline peripheral blood will be collected for myeloma response as well as for correlative biomarker analysis (timing of blood draws are defined in the flow chart in section 10.0).

Patients will be assessed for safety during routine visits, as well as treatment response using the standard International Myeloma Working Group (IMWG) Response Criteria (see Appendix II for IMWG Criteria) at **1 month** (shortly after completion of cycle 2 of pembrolizumab, anytime between **Day 23-30 +/- 7 days**), and **at least every 3 months +/-14 days (or as clinically indicated)**. Patients with stable disease or better per IMWG response criteria will continue with maintenance pembrolizumab (**200 mg/kg every 3 weeks for 2 yrs**). Patients that have progressive disease, or relapse after a complete response will be removed from the trial and will be treated per standard of care at the discretion of the treating physician.

Patients will continue to be monitored per standard of care on the trial. Patients will be monitored for known radiation related toxicity, known pembrolizumab toxicity, as well as any unexpected toxicity, per standard of care. PET/CT scans will be done at baseline and every 3 months, per standard of care.

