5. ADMINISTRATION OF STUDY PHARMACEUTICAL

In 2015, FDA approved Pembrolizumab (Keytruda) for the treatment of advanced melanoma and NSCLC patients; Pembrolizumab is a monoclonal antibody that targets the PD-1 receptor. Programmed death 1 (PD-1) (or CD279) is part of the CD28 family of proteins, which includes CTLA-4 and ICOS, that regulate T cell activity. PD-1 is a glycoprotein receptor that can be expressed on the surface of T cells, B cells and myeloid cells (monocytes and dendritic cells). In T cells, PD-1 expression is primarily induced by T cell receptor (TCR) engagement and ligation with PD-L1 and PD-L2, expressed on antigen presenting cells, and induces an inhibitory signal that antagonizes TCR signaling and other important pathways necessary for optimal T cell activation. Clinical trials with Pembrolizumab in advanced melanoma and NSCLC patients lead to approval by the FDA. Some efficacy in combination with lenalidomide for multiple myeloma has also been recently demonstrated. The recommended dose of Keytruda is 2mg/kg administered as IV infusion over 30 minutes every 3 weeks until disease progression, or unacceptable toxicity. Alternative dosing regimens are also available. The dose used on the Keynote -023 trial was 200 mg.

Dose Selection

Patients will receive pembrolizumab 200 mg IV delivered over a 30-minute period every 3 weeks until 2 years, or until disease progression, and/or unacceptable toxicity at the discretion of the treating physician. Infusions should be given over 30 minutes (not bolus or IV push).

Timing of Pembrolizumab Administration

Trial treatment should be administered on **Day 2 or 3 and then every 3 weeks +/- 7 days** after that as outlined in the Trial Flow Chart;

All trial treatments will be administered on an outpatient basis.

Pembrolizumab 200 mg will be administered as a 30 minute IV infusion every 3 weeks. Sites should make every effort to target infusion timing to be as close to 30 minutes as possible. However, given the variability of infusion pumps from site to site, a window of -5 minutes and +10 minutes is permitted (i.e., infusion time is 30 minutes: -5 min/+10 min).

The Pharmacy Manual contains specific instructions for the preparation of the pembrolizumab infusion fluid and administration of infusion solution.

Trial Blinding/Masking

This is an open-label trial; therefore, the Sponsor, investigator and subject will know the treatment administered.

Randomization Allocation

Not applicable

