9. TRIAL FLOW CHART

9.1 Study Flow Chart (Table 4: Trial Flow Chart)

Procedure	Pre- Treatment (within 28 days of starting)	Cycle 1, Day 1 week 1	Cycle 1, Day 2-3	Cycle 2, Day 22	q 3 WK cycles	q6 WK cycles x 2 yr or until progression	q 3 months (Rad Onc)	q 6 months
Initial Screening	X							
Informed Consent	X							
Inclusion/Exclusion	X							
Prior and Concomitant Medication	X							
Full Physical Examination	X			X				
Review of Systems	X			X		X	X	X
Vital Signs	X	X		X		X	X	X
Weight	X	X		X		X	X	X
ECOG Performance Status	X	X		X		X	X	X
HBcAb, HepC Ab	X							
*Bone Marrow Biopsy	X							X (clinical indication)
PET/CT	X						X	
Adverse effects Assessment	X			X	X (Pembro)	X	X	X
Labs								
Baseline Labs *	X							
Myeloma Labs *, LDH, ESR				X		X		
T3, FT4, TSH	X						X	
Pregnancy Test- urine or ser	X						X	
Urinanalysis	X						X	
uric acid, mg, phos, Coags (PTT,	X							
Correlative Biomarkers								
Serum markers (collect)	X	X (pre-RT)	X (Pre-PD1)	X (pre-PD1)		X (3,6 mo) (Pre-PD1)		
ExtraOssseous/Ossseous Biopsy* (clinical indication)								
Treatment								
*Pembrolizumab 200 mg IV			X	X	X			
RT (8 Gy/1fx)		X						
Survival Analysis								X
IMWG Assessment*	X						X	
CTCAE Toxicity*					X	X		

* EOS = end of study (at progression, or when patient stops being treated on the trial)

* Pembrolizumab 200 mg IV q3wk should be given for at least 2 yr and/or until progression.

* Baseline labs = CBC with Diff, CMP, calcium, Albumin, Serum Protein analysis, Quantitative Immunoglobulin, Serum Immunofixation (SIFE), 24 hr urine total protein, Urine Immune-Fixation, Serum Free Light Chain;

*Bone Marrow Biopsy (with IHC, flow, cytogenetics, FISH);

*Whole Body PET/CT every 3 months (as long as insurance approves);

*Biopsy of Osseous or extra-osseous site (if clinically indicated at baseline);

*Myeloma labs: (CBC with diff, CMP, Calcium, Quantitative Immunoglobulin, M-Protein (serum and Urine), Serum Free Light Chain;

* IMWG Assessment = Done at least during 1st month and every 3 months, or as clinically indicated;

*CTCAE Toxicity at the radiated site once at 3 months, 6 months, and 12 months;

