Treatment period will last from cycle 1, day 1 until disease progression and/or at least 24 months of pembrolizumab being delivered q3wks. Pembrolizumab 200 mg IV q3 weeks will be given for at least 2 years as described above or until disease progression. Safety evaluations should be conducted during the first day of every other cycle (minimum criteria), as detailed in the flow sheet in section 9.0. All AEs that occurred leading up to these treatment visits should be recorded. Post-Treatment Visits and all subsequent imaging and myeloma assessments will be per standard of care. All required blood and imaging will be per standard of care, except for the biomarker analysis, as outlined in section 9.0.

Safety Follow-Up Visit

The mandatory Safety Follow-Up Visit should be conducted approximately 30 days after the last dose of trial treatment or before the initiation of a new anti-cancer treatment, whichever comes first. All AEs that occur prior to the Safety Follow-Up Visit should be recorded. Subjects with an AE of Grade > 1 will be followed until the resolution of the AE to Grade 0-1 or until the beginning of a new anti-neoplastic therapy, whichever occurs first. SAEs that occur within 90 days of the end of treatment or before initiation of a new anti-cancer treatment should also be followed and recorded. Subjects who are eligible for retreatment with pembrolizumab may have up to two safety follow-up visits, one after the Treatment Period and one after the Second Course Phase.

Follow-up Visits

Subjects who complete treatment after 2 years or discontinue trial treatment for a reason other than disease progression should be assessed every 12 weeks (84 ± 14 days) or at physician's discretions by radiologic imaging to monitor disease. Subjects who show disease progression after the initial week 12 scan must have another assessment 4-6 weeks later by radiologic imaging to confirm evidence of disease progression. If disease progression is evident, treatment should be discontinued and subject should be assessed every 12 weeks (84 ± 14 days) by radiologic imaging to monitor disease status. Every effort should be made to collect information regarding disease status until the start of new anti-neoplastic therapy, disease progression, death, end of the study or if the subject begins retreatment with pembrolizumab as part of second phase enrollment. Information regarding post-study anti-neoplastic treatment will be collected if new treatment is initiated.

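### Pembrolizumab is written as 200 mg/kg in five treatment statements (Sections 1, 2 and 8), against the flat 200 mg every 3 weeks set elsewhere in the protocol

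*Combined protocol and SAP*

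**What the plan says.** Five current statements give the trial dose per kilogram:

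- Section 1, Protocol Summary, route of administration: "followed by pembrolizumab (200 mg/kg i.v. on day 2 or 3".
- Section 1, Protocol Summary, description of enrollment: "maintenance pembrolizumab (200 mg/kg every 3 weeks for 2 yrs".
- Section 2, Trial Overview, first dose: "200 mg/kg i.v. on day 2 or 3".
- Section 2, Trial Overview, maintenance: "200 mg/kg every 3 weeks for 2 yrs".
- Section 8, opening paragraph: "200 mg/kg i.v. on day 3".

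The other treatment statements give a flat dose:

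- Section 5, Dose Selection: "Patients will receive pembrolizumab 200 mg IV delivered over a 30-minute period every 3 weeks". The timing text in the same section repeats 200 mg.
- Section 9.1, flow chart footnote: "Pembrolizumab 200 mg IV q3wk should be given for at least 2 yr". The treatment row of the chart also shows 200 mg.
- Section 10, Enrollment and Treatment Period: "Pembrolizumab 200 mg IV q3 weeks will be given for at least 2 years".

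Section 4.3 argues for a fixed 200 mg dose from population pharmacokinetic simulations, and names fewer dosing errors as one advantage of fixed dosing. Section 10 defines an overdose as 1,000 mg or more.

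**The concern.** A dose of 200 mg and a dose of 200 mg/kg cannot both be the trial dose, and the protocol does not say which section governs. The wrong unit is not confined to background text. It stands in statements of how patients will be treated, including the summary and overview that staff may read first.

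The primary endpoint is toxicity at the irradiated site at 3 months, so the dose of the investigational drug should be free of doubt. A wrong unit in a summary can be carried into order sets, pharmacy documents or other study papers. It also works against the protocol's own reason for choosing a fixed dose.

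**Working it through.** **Inputs from the protocol**

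- Flat dose: 200 mg every 3 weeks (Sections 5, 9.1 and 10).
- Conflicting dose: 200 mg/kg (Sections 1, 2 and 8).
- Overdose threshold: 1,000 mg, described as at least 5 times the indicated dose for a 100 kg patient (Section 10).
- Highest dose in the cited Phase I trial: 10 mg/kg (Section 4.3).
- Supply: 100 mg in 4 mL solution, or 50 mg powder (Section 12, Table 7).
- Infusion time: 30 minutes (Section 5).

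**Assumption.** The protocol gives no weight distribution, so a range of 40 to 120 kg is used.

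**Step 1: the protocol's own figure.** The overdose multiple is threshold / dose = 1,000 / 200 = 5, so the stated multiple is reproduced with a flat 200 mg. It is also reproduced with 2 mg/kg in a 100 kg patient: 2 × 100 = 200 mg, and 1,000 / 200 = 5. The threshold therefore agrees with the flat dose but does not by itself prove it. It does rule out 200 mg/kg: 1,000 / 200 = 5 kg, so any patient of 5 kg or more would reach the overdose threshold at every infusion.

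**Step 2: the literal dose.** Dose = 200 mg/kg × weight.

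| | 40 kg | 120 kg |
|---|---|---|
| Literal dose | 200 × 40 = 8,000 mg | 200 × 120 = 24,000 mg |
| Multiple of the flat 200 mg | 8,000 / 200 = 40 | 24,000 / 200 = 120 |
| Multiple of the 1,000 mg threshold | 8,000 / 1,000 = 8 | 24,000 / 1,000 = 24 |
| 100 mg vials | 8,000 / 100 = 80 | 24,000 / 100 = 240 |
| Drug solution at 4 mL per vial | 80 × 4 = 320 mL | 240 × 4 = 960 mL |

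At the 100 kg used in the overdose definition, the literal dose is 200 × 100 = 20,000 mg, which is 100 times the flat dose and 20 times the threshold.

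**Step 3: against tested doses.** Per kilogram, 200 / 10 = 20 times the highest dose in the cited Phase I trial, at any weight.

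**Step 4: which dose is intended.** The section devoted to drug administration, the flow chart and the treatment-period text agree on 200 mg flat, and the rationale is written for a fixed dose. No rationale is offered for 200 mg/kg. The per-kilogram unit is the error.

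**The case against.** The strongest reply is that this slip corrects itself. The sections that govern dosing are right, Section 5 refers preparation to a Pharmacy Manual, and nobody would draw up 80 to 240 vials for a 30-minute infusion. Nothing in the documents shows that an order set or pharmacy document carries the wrong unit. The large multiples describe a reading that the rest of the protocol rejects. All of that is fair: the multiples show that the text is impossible as written, and they do not measure likely harm.

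It does not follow that the text can stay. A reader who sees that 200 mg/kg is impossible must still choose a correction, and the protocol offers a wrong one. Section 5 cites 2 mg/kg as the recommended dose, and the overdose definition refers to a 100 kg patient. Correcting to 2 mg/kg would give 2 × 40 = 80 mg to 2 × 120 = 240 mg in place of 200 mg. Section 4.3 suggests that exposures at 2 mg/kg and 200 mg are similar, so the clinical effect may be small, but it would still depart from the protocol dose.

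A second reply is that Section 4.3 is itself muddled, because it sets the fixed regimen beside a weight-based regimen that it also labels 200 mg. That is true, but the phrase is rationale text and not a sixth dosing instruction. The rest of that section supports the fixed dose.

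**Conclusion.** The concern holds and must be fixed. Five treatment statements in three sections carry a wrong unit for the investigational drug, and the intended dose is a flat 200 mg IV every 3 weeks.

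That the unit is wrong, and that the literal dose is 20 times the highest dose in the cited Phase I trial, does not depend on body weight. The figures of 40 to 120 times the flat dose and 8 to 24 times the overdose threshold rest on the assumed 40 to 120 kg.

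The severity comes from the kind of error, a dosing unit in treatment text of a safety trial. It does not come from any expectation that the literal dose would be given. The sample size, the primary endpoint and the confidence intervals do not change.

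**What to change.** Delete the per-kilogram unit in the five places: two in Section 1, two in Section 2 and one in Section 8. Every treatment statement should then read as 200 mg IV, given every 3 weeks. Check that order sets and pharmacy documents match.

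The 1,000 mg overdose threshold stays. The reference to a 100 kg patient can be dropped, since the indicated dose no longer depends on weight.

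The same amendment can make three editorial corrections, none of which bears on the verdict: align the day in Section 8 with the day 2 or 3 given elsewhere, tidy the weight-based wording beside 200 mg in Section 4.3, and remove the leftover sentence there about Cohorts A to D.

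The cost is five wording changes in an amendment and one check of dependent documents, with no change to design, sample size or analysis.
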